5.2 Exclusion Criteria

An individual who meets any of the following criteria will be excluded from participation in this study:

1. MS clinical relapse or use of high dose of steroids in the past month
2. Adhering to prescribed medical marijuana use in accordance with clinician's guidelines
3. Alcohol, tobacco, or substance use disorder other than cannabis
4. Primary neurologic, psychiatric or other medical disorder other than MS
5. Currently meets DSM-V criteria for moderate or severe substance use disorder in the past 6 months for any psychoactive substance.
6. Meets DSM-V criteria for current panic disorder, obsessive-compulsive disorder, post-traumatic stress syndrome, bipolar affective disorder, schizophrenia, dissociate disorders, and any other psychotic disorder or organic mental disorder
7. Current suicidal ideation or deemed to be of potential risk of self-injury
8. History of traumatic brain injury
9. Seizure disorder or recent (<5 years) seizure history
10. Metal implants in the head or neck
11. Enrolled in group or individual therapy for substance use disorder concurrent to intervention
12. Any skin disorder or skin sensitive area near stimulation locations
13. Pregnant or breastfeeding

Exclusion criteria may be confirmed through medical records, screening assessments and self-report.

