This material is the property of the NYU School of Medicine and Langone Medical Center. Do not disclose or use except as authorized in writing by the study sponsor
Interventional Template Version: 11 January 2019

PANAS	Positive and Negative Affect Schedule
PDDS	Patient Determined Disability Scale
PI	Principal Investigator
QA	Quality Assurance
QC	Quality Control
RAVLT	Rey Auditory Visual Learning Test
RRMS	Relapse Remitting Multiple Sclerosis
SAE	Serious Adverse Event/Serious Adverse Experience
SDMT	Symbol Digit Modalities Test
SOP	Standard Operating Procedure
STAI	State-Trait Anxiety Inventory
tDCS	Transcranial Direct Current Stimulation
TLFB	Timeline Followback Method Assessment
US	United States
TMS	Transcranial magnetic stimulation

CONFIDENTIAL

This material is the property of the NYU School of Medicine and Langone Medical Center. Do not disclose or use except as authorized in writing by the study sponsor
Interventional Template Version: 11 January 2019

Protocol Summary

Title	A Telehealth tDCS Approach to Decrease Cannabis Use: Towards Reducing Multiple Sclerosis Disability
Short Title	A Telehealth tDCS Approach to Decrease Cannabis Use in MS
Brief Summary	We will recruit 52 patients with MS, CUD, and elevated distress (K10 score 10-35) in a double-blinded, parallel-arm, sham-controlled trial of a completely at-home intervention. We will test 20x20-minute RS-tDCS (2.0 mA, DLPFC: left anodal) paired with guided mindfulness meditation to decrease distress and cannabis use. Participants will be randomized 2:1 to active vs. sham tDCS.
Phase	Phase 2
Objectives	
- Evaluate the effect of DLPFC tDCS to decrease distress component of cannabis use disorder- Evaluate the effect of DLPFC tDCS to reduce cannabis use- Evaluate if DLPFC tDCS related change in cannabis use is linked to a change in distress
Methodology	2:1 Randomized, Parallel-Arm, Double-Blind, Sham-Controlled Design
Endpoint	
Primary Endpoints:
 
- Decrease in Distress by treatment End- Decrease in Cannabis Use by treatment End 
Secondary Endpoints:
 
-Decrease in Distress through 3-month follow-up-Decrease in Cannabis Use through 3-month follow-up
Study Duration	2 years
Participant Duration	Approximately 4.5 months (4-6 weeks of intervention + follow-ups at 1, 2, and 3 months)
Duration of IP administration	20x20 minutes daily sessions of DLPFC tDCS combined with mindfulness meditation

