Population	N=52 female participants (ages 21-65) with RRMS and CUD
Study Sites	NYU Langone Health [name]
Number of participants	N=52 participants expected to be enrolled at NYU Langone Health
Description of Study Procedure	
tDCS is noninvasive brain stimulation device that modulate brain activity delivering a low-intensity electrical current (2.0 mA) through scalp sponge electrodes. Participants will follow an audio track for guided mindfulness during the stimulation.
 
For Active tDCS, the device is programmed to ramp up to 2.0 mA (for 30 seconds), provide constant current throughout session (19 minutes), and then ramp down (for 30 seconds) at the end.
 
For Sham tDCS the device is programmed to ramp up to 2.0 mA (for 30 seconds) followed by a ramp down (30 seconds), with no current delivery for 18 minutes, and then ramp up (for 30 seconds) and down (for 30 seconds) at the end.

Reference Therapy	

CONFIDENTIAL

This material is the property of the NYU School of Medicine and Langone Medical Center. Do not disclose or use except as authorized in writing by the study sponsor

[figure not shown]
Interventional Template Version: 11 JAN 2019

Key Procedures	Active or sham tDCS with simultaneous mindfulness meditation
Statistical Analysis	Multivariate linear regression will be used to evaluate the outcome of each Aim. The dependent measures will be nested within timepoint (Visit 1, 5, 10, 15, 20), with active/sham as fixed effects.

CONFIDENTIAL

This material is the property of the NYU School of Medicine and Langone Medical Center. Do not disclose or use except as authorized in writing by the study sponsor
Interventional Template Version: 11 January 2019

SCHEMATIC OF STUDY DESIGN

CONFIDENTIAL

This material is the property of the NYU School of Medicine and Langone Medical Center. Do not disclose or use except as authorized in writing by the study sponsor
Interventional Template Version: 11 January 2019

1 Key Roles

[name], Principal Investigator
NYU Langone Health — Neurology
[name]
[contact]
[contact]

[name]
NYU Langone Health — Neurology
[name]
[contact]
[name]

[name]
Wake Forest School of Medicine
[name]
[contact]
[contact]

2 Introduction, Background Information and Scientific Rationale

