5.1 Inclusion Criteria

In order to be eligible to participate in this study, an individual must meet all of the following criteria:

1. Ages 21-65 (inclusive)
2. Female
3. Seeking treatment to reduce or discontinue current cannabis use (smoke/vape/ingest)
4. Current Cannabis Use Disorder per DSM-V
5. K10 score 10-35, inclusive (mild to high moderate distress)
6. Definite MS diagnosis, relapsing remitting (RRMS) subtype
7. PDDS score 0-7 (mild to moderate neurological disability, established to be able to complete procedures)
8. All medications stable for \geq 1 month prior to enrollment and throughout the trial
9. Ability to understand the informed consent process and provide consent to participate in the study
10. Stable and continuous access to internet service, email (WiFi “hotspot” to be provided if needed)
11. Ability to use mobile devices
12. Fluent in English language (due to outcomes validated in English versions only)
13. WRAT-4 score \geq 85

Inclusion criteria may be confirmed through medical records, screening assessments and self-report.

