10.2 Statistical Hypotheses

We will test the hypotheses that there is an interaction between treatment (active vs. sham) and time on 1) distress (K10 & PANAS-NA) and 2) use (TLFB), with additional outcomes addressing mood/anxiety (BDI, STAI), detailed cannabis use (DFAQ-CU), craving (MCQ-17) and withdrawal (CWS).

If the interaction effect for an outcome is significant, we will conclude there is statistical evidence of overall treatment effect. If the spaghetti plots suggest trends (e.g., linear, quadratic, or piecewise changes) we will treat time as a continuous variable and fit repeated measures regression models along with group and its interaction with continuous time as independent variables.

In supplementary analyses, additional factors or covariates will be included in the models (along with their corresponding interactions with group and time) to examine the potential influence of gender, age, MS disability (PDDS), depressive symptoms (BDI), anxiety (STAI) and CUD severity (CUDIT-R) on responsiveness to active vs. sham treatment.

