10.4.2.1 Missing Data

We will perform attrition analyses on whether participants and dropouts differ on key variables (severity of cannabis use disorder or CUD, as measured by the CUDIT-R) and whether variables on which they differ interact with treatments to affect outcome measures. As participants will be randomized to treatment, it is unlikely that missing data will produce biased estimates of treatment effect, as observed and unobserved covariates should theoretically be balanced across treatment groups. Larger proportions of data missing at random (MAR) or missing not at random (MNAR) could potentially bias study findings and reduce power. Should substantial proportion of cases (over 10%) for a critical independent variables and evidence of non-randomness, missing data will be incorporated using multiple imputation methods and inverse probability weighting. Results will be examined in patients who completed at least one of their randomized assigned intervention sessions as supportive analyses. First the distribution of the missing indicator variable given the observed data is modeled to derive a propensity score. Then observations are grouped on these propensity scores and an approximate Bayesian bootstrap multiple imputation is applied to each group. This has previously been identified as a fruitful method in other addiction treatment research [Witkiewitz et al., 2015, *Addiction*, "Pain as a predictor of heavy drinking and any drinking lapses in the COMBINE study and the UK Alcohol Treatment Trial"].

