14.3 Protocol Deviations

A protocol deviation is any noncompliance with the clinical trial protocol, GCP, or Manual of Procedures (MOP) requirements. The noncompliance may be either on the part of the participant, the investigator, or the study site staff. As a result of deviations, corrective actions are to be developed by the site and implemented promptly.

These practices are consistent with ICH E6:

- 4.5 Compliance with Protocol, sections 4.5.1, 4.5.2, and 4.5.3
- 5.1 Quality Assurance and Quality Control, section 5.1.1
- 5.20 Noncompliance, sections 5.20.1, and 5.20.2.

It is the responsibility of the site PI/study staff to use continuous vigilance to identify and report deviations within 10 working days of identification of the protocol deviation, or within 10 working days of the scheduled protocol-required activity.

All protocol deviations must be addressed in study source documents and reported to the local IRB per their guidelines. The site PI/study staff is responsible for knowing and adhering to their IRB requirements. Further details about the handling of protocol deviations will be included in the MOP.

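### Exclusion 5 lacks the cannabis exception given in exclusion 3, so as written it limits cannabis use disorder to below moderate, a limit absent from inclusion 4 and the population summary

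*Combined protocol and SAP*

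**What the plan says.** Section 5.1, inclusion 4, asks for "Current Cannabis Use Disorder per DSM-V" and sets no severity limit.

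Section 5.2 excludes a person who meets any one item on its list. Two items concern substance use disorders:

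- Exclusion 3: "Alcohol, tobacco, or substance use disorder other than cannabis". It applies at any severity and excepts cannabis.
- Exclusion 5: "Currently meets DSM-V criteria for moderate or severe substance use disorder in the past 6 months for any psychoactive substance". It is limited to the two higher grades, mentions a 6-month period, and has no cannabis exception.

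The Protocol Summary describes the population without a grade of CUD. The Population row reads "N=52 female participants (ages 21-65) with RRMS and CUD", and the Brief Summary likewise names MS, CUD and distress.

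Under Section 8.3.2 a clinician checks the criteria at Visit 1, after consent, and a device is randomized only for those found eligible. Section 5.7.1 allows an investigator to end participation when an exclusion criterion arises, or is first recognized, after entry. Section 14.3 states: "A protocol deviation is any noncompliance with the clinical trial protocol, GCP, or Manual of Procedures (MOP) requirements". Section 19 lists the eligibility and verbal screen checklists as documents held and changed outside the protocol.

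**The concern.** The trial exists to treat people with CUD, yet one of its exclusions, taken at its word, removes everyone whose CUD is moderate or severe. Neither the inclusion criteria nor the population summary tells the reader of such a limit. Two staff members following the same protocol could reach opposite decisions on a woman with moderate CUD: inclusion 4 admits her and exclusion 5 rejects her.

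At stake is the population to which the result applies. Section 10.4.2 says the study is meant to supply effect sizes for a later grant application. If the criterion is applied literally, those effect sizes describe CUD below moderate and not the population in the summary. If it is applied with an unwritten exception, the trial accumulates eligibility deviations.

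**Working it through.** The plan gives no figure to reproduce here, so the check sets the criteria side by side.

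**Step 1: does exclusion 5 reach cannabis?** Its scope is any psychoactive substance. By excepting cannabis, exclusion 3 shows that the list counts CUD as a substance use disorder. Because meeting any single item excludes, the exception in exclusion 3 does not carry over to exclusion 5. Literally, then, moderate or severe CUD is covered.

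**Step 2: who is affected under each reading?** Every person below meets inclusion 4.

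| Person | Exclusion 3 | Exclusion 5, literal | Exclusion 5, cannabis excepted |
|---|---|---|---|
| CUD below moderate only | not excluded | not excluded | not excluded |
| CUD moderate or severe only | not excluded | **excluded** | **not excluded** |
| CUD plus another current use disorder | excluded | excluded if either is moderate or severe | excluded if the other is moderate or severe |
| CUD below moderate, plus a moderate or severe disorder of another substance within 6 months but no longer current | not excluded, if exclusion 3 means current disorders | excluded, if the 6-month wording is a look-back | excluded, on the same condition |

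The two readings lead to different decisions only in the second row. In the third row exclusion 3 has already removed the person. So for current disorders:

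- the literal reading gives exclusion 5 one added effect, the removal of moderate and severe CUD;
- the excepted reading gives it no added effect.

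The fourth row shows that the 6-month wording may still give exclusion 5 separate work for recently remitted disorders of other substances.

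**Step 3: what follows from each reading?** Literal: only CUD below moderate can be enrolled, which is narrower than inclusion 4 and the summary. Excepted: each enrolled participant with moderate or severe CUD departs from the written protocol, which Section 14.3 defines as a deviation.

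**Step 4: when does it act?** Exclusion 5 is checked at Visit 1, before a device is randomized, so it acts mainly on who enters. Some exits come after randomization: Section 8.1 has devices shipped before the tolerability test and the baseline urine test, and either can end participation. Those exits do not involve exclusion 5. The only route by which exclusion 5 could act after randomization is discretionary termination under Section 5.7.1.

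**Step 5: how large is the effect?** The documents give no distribution of DSM grade, so neither the number nor the share of candidates affected can be computed. The room for loss is known. Section 5.6 counts enrolment from consent and plans about 52 enrolled to give 42 evaluable: 52 − 42 = 10 places to spare, which Section 4.1 assigns to screen failures and withdrawals. Each failure on exclusion 5 after consent uses one of them.

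**The case against.** The strongest reply is that exclusions normally narrow inclusions. A brief summary omits most criteria, so its silence on grade is not by itself a contradiction. In a trial that requires CUD and treatment-seeking, an investigator would readily take exclusion 5 to mean other substances. Overlap between items in such a list is common, and the 6-month wording may give exclusion 5 a purpose of its own under that reading. This shows that the excepted reading is plausible. It does not supply the exception, which no section of the protocol contains, and the checklists that might contain it are not available.

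Four stronger inferences are tempting and are not supported.

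- *That nobody can be enrolled.* A person with CUD below moderate meets inclusion 4 and is not caught by exclusion 5.
- *That the treatment comparison is biased.* The criterion is assessed before randomization. Termination under Section 5.7.1 is a possible exception, but it is discretionary and nothing shows it would be used this way.
- *That the planned severity analyses prove no cap was meant.* Section 10.2 examines age, disability and other factors "and CUD severity (CUDIT-R) on responsiveness to active vs. sham treatment", and Section 10.4.2.1 compares dropouts on "severity of cannabis use disorder or CUD, as measured by the CUDIT-R". Both use the CUDIT-R score, not the DSM grade. Scores can vary within a capped population, so these sections do not settle which reading is meant.
- *That routine monitoring will reveal any misapplication.* The meetings in Section 9.7.1 review screen failures. But Sections 5.4 and 8.3.1 require pre-screen data on ineligible people to be destroyed at once, so rejections made by telephone leave nothing to review.

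**Conclusion.** The point holds as an inconsistency between a stated rule and the stated population. Following exclusion 5 as written enrols only CUD below moderate, a limit that neither inclusion 4 nor the Protocol Summary gives. Following it with cannabis excepted puts each participant with moderate or severe CUD in breach of a written exclusion. The consequence lies mainly in who is enrolled, to whom the result applies, and recruitment. No effect on power, endpoints or the analysis model is shown, and the number of people affected is unknown.

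The conclusion rests on the text of Sections 5.1 and 5.2 and on CUD counting as a substance use disorder, as exclusion 3 itself assumes. It would carry less practical weight if the checklists already record an exception, but they do not amend the protocol.

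**What to change.** The sponsor should reconcile inclusion 4 with exclusions 3 and 5 so that one population is stated throughout. There are two ways to do this, and the choice is the sponsor's: except cannabis in exclusion 5 as in exclusion 3, or state the severity limit openly in inclusion 4 and the Protocol Summary. If the 6-month wording is meant to cover recently remitted disorders of other substances, it would help to say so in the same amendment.

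The eligibility and verbal screen checklists should then be aligned with the amended text. Any post-consent screen failures, and any terminations under Section 5.7.1, that were attributed to exclusion 5 should be reviewed. The review should note that pre-screen rejections leave no data and cannot be recovered.

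The cost is a few words in a protocol amendment, a check of two checklists and a short file review. No study visits are added. If a severity limit is intended, the recruitment pool is narrower than the summary suggests, by an amount the documents do not allow anyone to compute.

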5.3 Vulnerable Subjects

Vulnerable subjects will not be enrolled in this study. MS patients do not require additional cognitive screening to determine capacity to consent beyond the process described in section 13.3.2.1. [name], is a practicing clinical neuropsychologist who specializes in the treatment of cognitive symptoms of

CONFIDENTIAL

This material is the property of the NYU School of Medicine and Langone Medical Center. Do not disclose or use except as authorized in writing by the study sponsor
Interventional Template Version: 11 January 2019

MS. MS can affect cognition mildly, however it is rare for MS patients to present with global cognitive impairment that would impact their capacity to provide informed consent.

5.4 Strategies for Recruitment and Retention

The MS Comprehensive Care Center (MSCCC) at NYU Langone Health has an extensive recruitment base. Patients who are seen by NYU medical staff, who fit the eligibility criteria, will be referred for the study by the study PI and sub-investigators. All physicians and medical staff at the MSCCC will be presented with the study description.

A patient who is seeing one of these medical staff members as their treating physician will be introduced to the study by that medical staff member. If the patient is interested and agrees to be contacted, a team member will contact them on the phone (or in-person if participant is already in clinic) using an IRB-approved phone script to provide additional study information and pre-screen to assess eligibility. Verbal responses will be recorded on a separate pre-screen verbal checklist. For any subject who is ineligible, or who is eligible but decides not to participate, we will immediately destroy the data collected during the pre-screen.

An IRB approved flyer will be posted in local physician offices and waiting rooms and throughout NYU, the surrounding community and support organizations. In addition to recruitment at NYU's MSCCC, we will post these flyers around the Ambulatory Care Center (ACC) for patients to recruit from the entirety of the Neurology department and from any number of people who come to visit the ACC on [name] or have an appointment at [name].

An IRB approved study description will be posted on MS related websites and shared with appropriate list-services related to those websites.

BuildClinical marketing services will also be used to facilitate nationwide recruitment. Advertisements will be placed in various platforms. Prospective participants will click on the ad and be directed to the landing page to complete a screening form. A notification message will be sent to the study team upon completion of the form to review and connect with prospective participants.

5.5 Duration of Study Participation

Study participation will last approximately 4.5 months and will include:

- Remote consent (20 minutes), with participant provided as much time as they need to review consent form. Once consented, participant will be scheduled for telehealth research screening. The screening will be scheduled based on participant and study/clinician availability, which can occur on the same day as consent and anticipated to be within two days of consent.
- Telehealth research screening (1 hour).
- Baseline & tDCS Session 1 (approximately 2 hours: 20 minutes to orient to device, 1 hour assessments, 20 minute tDCS session).
- tDCS treatment sessions (20 x 20 min session over 4-6 weeks)
 - Sessions 5, 10, and 15 will be 45 minutes (20 minute session +25 minutes questionnaires)
- tDCS Session 20 & Treatment-end (1.5 hours)
- 1 month Follow-up (1 hour)
- 2 month Follow-up (1 hour)
- 3 month Follow-up (1 hour)

5.6 Total Number of Participants and Sites

Recruitment will end when approximately 52 participants are enrolled (sign consent). It is expected that approximately 52 participants will be enrolled in order to produce 42 evaluable participants.

CONFIDENTIAL

This material is the property of the NYU School of Medicine and Langone Medical Center. Do not disclose or use except as authorized in writing by the study sponsor
Interventional Template Version: 11 January 2019

